Adverse events ¹⁷	X	X	X				X				X		X	
Study treatment														
Enrolment ¹⁸		X												
NMS-01940153E infusion ¹⁹			X	X	X		X	X	X					
Disease assessment														
Tumor imaging ²⁰	X								X*		X		X	
BCLC and TNM staging ²¹	X													
Survival follow up ²²											X		X	
Investigational assessments														
Biomarkers sampling ²³		X												
PK blood sample ²⁴			X°	X°	X°	X°	X°		X°	X°				

See Footnotes for Schedule of Events on following page

Footnotes for Phase II Schedule of events
1. Informed consent: to be obtained before the starting of any trial related procedure; it may occur also before the 28-days screening period. After signature, a subject Screening number is assigned centrally.
2. Relevant medical/oncologic history: to be assessed at screening, within 7 days from treatment start. Medical history includes history of relevant medical conditions and concomitant illnesses either present (active or controlled) or resolved. Oncologic history includes information on initial diagnosis, prior regimens and best response to prior regimens.
3. Physical examination and ECOG PS: to be recorded at screening, within 7 days from treatment start; on day 1 of each treatment cycle (before treatment administration); at EoT and at 28-days follow up.
4. Weight (kilograms): to be recorded at screening, within 7 days from treatment start, and on day 1 of each treatment cycle (before treatment administration).
5. Temperature (Celsius degree): to be recorded at screening, within 7 days from treatment start, and on days 1, 8, 15 of each treatment cycle (before treatment administration).
6. Blood pressure and heart rate: to be recorded at screening, within 7 days from treatment start; on days 1, 8, 15 before the treatment start and within 30 minutes after the end of infusion; at EoT and 28-days follow up. At each determination, if SBP > 150 mmHg and/or DBP > 95 mmHg is registered, repeat determinations two more times at 30 minutes interval.
7. Gastro-esophageal endoscopy: to be performed to all patients with known history of gastro-esophageal varices. For these patients the assessment is mandatory, at screening within 7 days from treatment start, unless an endoscopy is available within 3 months before the treatment start. For all other patients the assessment is not required, granted that an endoscopy is available within 24 months before the treatment start, or PI would justify the absence of clinical need for this assessment;
8. 12-lead ECG (12-lead, in triplicate, includes qualitative and quantitative assessment): to be performed to determine QT interval using Fridericia standard (QTcF) at screening, within 7 days from treatment start, at cycle 1 day 1 (first dose) and at cycle 1 day 15 (dose 3) triplicate ECG will be collected prior to dosing (30 min before the start of infusion and at least 10 minutes after any blood drawn or intravenous access procedure) and at peak concentration, prior to and as close as possible to the PK timepoint planned 5 minutes before the end of infusion (e.g. ≤ 10 minutes),, and at EoT visit. To be repeated at any time it is medically indicated. If the ECG assessment is not feasible on cycle 1 day 1 or cycle 1 day 15, a different timing or other solutions should be discussed with Sponsor. Additional assessments to be performed if clinically indicated. At each time point, three consecutive supine 12-lead ECGs will be performed approximately 2 minutes apart to determine mean QT interval using Fridericia standard (QTcF). The following parameters will be collected: sinus rhythm, heart rate, RR interval, PR interval, QRS interval, QT interval and QTcF interval. For all patients enrolled in the study, the Sponsor may request the ECG tracing and reports collected during the study be submitted to a third-party for retrospective independent review of the ECGs reading and interpretation.
9. Pregnancy test (serum/urine): for women of childbearing potential only, to be performed at screening, within 72 hours from treatment start, on day 1 of each treatment cycle (before treatment administration) and at EoT visit.
10. Serology: in case of positive HBV anamnesis, includes HBV DNA; in case of positive HCV anamnesis, includes HCV RNA; in case of HBV unknown anamnesis, includes HbsAg, HbeAg, HbcAg, Anti-HBc-IgM; in case of HCV unknown anamnesis, includes liver function test as by local standards and HCV Ab. Anti-HIV test. To be performed at screening, within 7 days from treatment start.
11. Hematology: includes hemoglobin (Hb), red blood cells (RBC), platelet (PLT) and white blood cells (WBC) with differential count (neutrophils, lymphocytes, monocytes, eosinophils and basophils). To be performed at screening, within 7 days from treatment start; on cycle 1 , on days 1, 8, 15, 22; from cycle 2 onward , on days 1, 8, 15; at cycle 2 , in case neutropenia Grade ≥2 is observed, repeat the hematological evaluation also at day 22; at EoT and 28-days follow up. A time window of -1 day is allowed; on days of treatment administration, sampling should be performed and results should be available before the start of NMS-01940153E infusion. In case of cycle delay due to toxicity and/or if clinically indicated, additional assessments should be done as per Investigator judgment.
12. Blood chemistry: includes glucose, electrolytes (Na, K, Ca, P, magnesium), urea or BUN, serum creatinine, creatinine clearance (calculated with Cockroft-Gault equation), total protein, albumin, aspartate aminotransferase (AST/SGOT), alanine aminotransferase (ALT/SGPT), gamma-glutamyl transferase (γ-GT), total bilirubin, unconjugated bilirubin, alkaline phosphatase (ALP), lactate dehydrogenase (LDH). To be performed at screening, within 7 days from treatment start; on cycle 1 , on days 1, 8, 15, 22; from cycle 2 onward , on days 1, 15; at EoT and 28-days follow up. A time window of -1 day is allowed; on days of treatment administration, sampling should be done and results should be available before the start of NMS-01940153E infusion. In case of cycle delay due to toxicity and/or clinically indicated, additional assessments should be done as per Investigator judgment.
13. Coagulation: includes international normalized ratio (INR) of prothrombin. To be performed at screening, within 7 days from treatment start; on cycle 1 , on days 1, 8, 15, 22; from cycle 2 onward , on days 1, 15; at EoT and 28-days follow up. A time window of -1 day is allowed; on days of treatment administration, sampling should be done and results should be available before the start of NMS-01940153E infusion. In case of cycle delay due to toxicity and/or clinically indicated, additional assessments should be done as per Investigator judgment.
14. AFP: to be performed at screening, within 7 days from treatment start; at the end of even cycles and at EoT. A time window of -2/+5 days is allowed.
15. Urinalysis: includes pH, glucose, protein and blood. To be performed at screening, within 7 days from treatment start and at EoT. To be repeated as medically indicated.

16. Concomitant medications: includes all treatment, supportive care taken (started or completed), transfusion, procedures and hospitalization up to 28 days before treatment start. Once the patient has ended the study treatment, concomitant medications should be recorded for 28 days (in case, up to 35 days) after the last on-study treatment administration or until all study drug-related toxicities have resolved, whichever comes first, or until alternative anticancer therapy is initiated. In this case, the reporting period will end at the time the new treatment is started.
17. Adverse events: to be documented at each scheduled visit since patient signs the Informed Consent until 28 days after the last treatment administration, or until all serious or study drug-related toxicities have resolved or are determined to be "chronic" or "stable", whichever comes first, or until alternative anticancer therapy is initiated. In this case, the reporting period will end at the time the new treatment is started.
18. Enrolment: the investigator request of subject enrolment is the guarantee that all the eligibility criteria are met; Enrolment number is assigned centrally. It is recommended to start the treatment within 1-4 days from patient enrolment.
19. NMS-01940153E infusion: patients will receive treatment with NMS-01940153E administered as IV infusion for 3 consecutive weeks on days 1, 8, 15 followed by 1 week of rest, in a 28-day cycle. The duration of infusion will be dependent on the total dose to be administered: 1 hour infusion if ≤ 255 mg are administered; 1 hour 30 minutes infusion if >255 mg but <375 mg are administered. Within one cycle, in case the patient cannot be retreated on the day foreseen because of toxicity, the dose will be skipped, and the patient will be retreated at the next foreseen time-point. Dose reduction/omission is foreseen based on toxicities observed. Patients that cannot be retreated, for any reason, within 1 week from day 28 will go off-treatment, unless the investigator believes treatment continuation is in the patient best interest. In this case a maximum delay of 2 weeks (up to day 42 from cycle start) will be allowed. Otherwise patients may continue on investigational drug until a withdrawal criterion is met.
20. Tumor imaging: to be performed at screening, within 28 days from treatment start (in case a tumor imaging is already available in the specified time window, it has not to be repeated); at the end of even months (even cycles) of treatment and at EoT. The EoT assessment is to be performed only if it was not performed in the previous 4 weeks. In patients withdrawn for reasons other than progressive disease (PD), during follow up, tumor assessment should be performed every 2 months, until PD or until a new antitumor therapy starts. On treatment, a time window of -2/+5 days is allowed. Patients with responding tumors (complete or partial response) must have response confirmed by CT scan at least 4 weeks after the 1 st documentation of response. The same method of assessment and technique should be used to characterize and follow the same lesion at screening, during treatment and at EoT. Ct scan is the desirable method for lesion measurement (see Section 11.3.1).
21. BCLC and TNM Staging: TNM and BCLC staging will be requested at enrollment for all patients, including collection of clinical related additional info
22. Survival follow up: post-treatment survival status, including additional information (e.g. new anticancer therapy), will be collected at the 28-days follow up visit and thereafter every 2 months from last treatment administration until death. Telephone contacts are acceptable for these assessments.
23. Biomarkers sampling: peripheral blood samples will be collected at Enrollment (≤ 7 days before Cycle1 Day1) for analysis of selected molecular alterations in circulating free DNA (cfDNA) from plasma
24. PK blood sample: during the Phase II, a sparse sampling procedure will be adopted; blood sampling for PK is to be performed at cycles 1, 2, 3 and 4 (refer to Table 5 for details).
25. End of Treatment (EoT): visit to be performed within 7 days from the decision of discontinuing the study drug.
26. Off treatment assessments: 28 days, and no more than 35 days, after discontinuation of study treatment patients will return for the following assessments: ECOG PS, blood pressure and heart rate, hematology, blood chemistry, coagulation, concomitant medications, adverse events and survival follow up. Further follow up contacts will be scheduled every 2 months from last treatment administration, until death, to assess the survival status, including possible additional information.
28 day follow up for laboratory abnormalities: in case hematology, blood chemistry, coagulation, study drug-related and clinically significant abnormalities persist beyond the 28-days follow up assessment, they should be followed until they resolve or the Investigator assess them as chronic or stable, or until alternative anticancer therapy is initiated. In this case, the reporting period will end at the time the new treatment is started.
28 days follow up for adverse events: the AEs reporting period ends 28 days after the last study treatment administration. The following events should be followed after the end of the reporting period: serious adverse events (SAEs) with outcome "not recovered" or "unknown" and study drug-related AEs with outcome "not recovered" or "unknown". They have to be followed until they resolve or the Investigator assess them as chronic or stable, or until alternative anticancer therapy is initiated. In this case, the reporting period will end at the time the new treatment is started.
* Cycle 1 Day 1 assessments: evaluations do not need to be repeated before study drug administration if they were performed at screening within 24 hours from treatment start.
• only even cycles

Table 5. Investigational Assessments details for Phase II

	Cycle 1 (Days)								Cycles 2 and 4 (Days)						Cycle 3 (Days)					
	D1			D8		D15			D22	D1	D15			D26 - 28		D15				
Timing related to EoI (hour)	0.0 [§]	15min – 2h	>2h – 6h	Pre	0.0 [§]	Pre	0.0 [§]	15min – 2h	>2h – 6h	Any	Pre	Pre	0.0 [§]	15min – 2h	>2h – 6h	Any	Pre	0.0 [§]	15min – 2h	>2h – 6h
PK blood sample ^c	X	X ^{Od}	X ^{Ev}	X ^{Od}	X ^{Ev}	X	X	X ^{Ev}	X ^{Od}	X	X	X	X	X ^{Od}	X ^{Ev}	X	X	X ^{Ev}	X ^{Od}	

c. **PK blood samples:** all patients enrolled in the Phase II portion of the study will undergo blood draws for PK analysis (central laboratory) based on their enrollment number (odd or even), as detailed below.

Odd patients (X^{Od})

Cycle 1:

Day 1: 5 minutes before the end of infusion (0.0§), from 15 minutes to 2h after the end of study drug administration

Day 8: before the start of infusion (pre-dose)

Day 15: before the start of infusion (pre-dose), 5 minutes before the end of infusion (0.0§), from >2h to 6h after the end of study drug administration

Day 22: one sample, at any time

Cycles 2 and 4:

Day 1: before the start of infusion (pre-dose)

Day 15: before the start of infusion (pre-dose), 5 minutes before the end of infusion (0.0§), from 15 minutes to 2h after the end of study drug administration

One samples on day 26 or day 27 or day 28, at any time.

Cycle 3:

Day 15: before the start of infusion (pre-dose), 5 minutes before the end of infusion (0.0§), from >2h to 6h after the end of study drug administration

Even patients (X^{Ev})

Cycle 1:

Day 1: 5 minutes before the end of infusion (0.0§), from >2h to 6h after the end of study drug administration

Day 8: 5 minutes before the end of infusion (0.0§)

Day 15: before the start of infusion (pre-dose), 5 minutes before the end of infusion (0.0§), from 15 minutes to 2h after the end of study drug administration

Day 22: one sample, at any time

Cycles 2 and 4:

Day 1: before the start of infusion (pre-dose)

Day 15: before the start of infusion (pre-dose), 5 minutes before the end of infusion (0.0§), from >2h to 6h after the end of study drug administration

One samples on day 26 or day 27 or day 28, at any time.

Cycle 3:

Day 15: before the start of infusion (pre-dose), 5 minutes before the end of infusion (0.0§), from 15 minutes to 2h after the end of study drug administration

Note: blood pressure is to be taken on days 1, 8, 15 before the treatment start and within 30 minutes after the end of infusion, before the blood sample for PK is taken (if the case).

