11.5.1.4. Adverse Event Reporting Period

The adverse event reporting period for this trial begins upon signing of informed consent and ends 28 days after the last study treatment administration.

However, if a patient begins a new anticancer therapy earlier than 28 days after the last dose of study treatment administration, the adverse event reporting period will end at the time the new anticancer therapy starts.

All the adverse events that occur in trial patients during the adverse event reporting period must be reported to the Sponsor, whether or not the event is considered related to the study treatment.

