11.5.1.5. Adverse Event Follow Up after the End of the Reporting Period

The following events should be followed after the end of the reporting period (i.e., 28 days after the last study treatment administration):

1. SAEs with outcome ‘not recovered’ or ‘unknown’ at the end of the reporting period.
2. Non-serious events classified as related to the investigational study treatment with outcome ‘not recovered’ or ‘unknown’ at the end of the reporting period.

These events should be followed until they resolve or until the Investigator determines, whenever possible, that they have become “chronic” or “stable”. Resolution of such events is to be documented on the SAE Form and/or on e-CRF.

In addition, if after the end of the reporting period, suspected serious adverse reactions or deaths are reported to the Investigator and he/she believes that they are related to the IMP, it is the Investigator’s responsibility to report these suspected serious adverse reactions to the Sponsor. Such suspected serious adverse reactions will be reported using a Serious Adverse Event Report or by any other way chosen by the Investigator.

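### Footnote 17 of the Schedule of Events lets adverse event recording end before day 28 after the last dose, against section 11.5.1.4, section 10 and the Schedule's own closing notes

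*Protocol*

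**What the plan says.** Protocol section 7, footnote 17 of Tables 2 and 4, has adverse events documented at each scheduled visit from consent to day 28 after the last dose, "or until all serious or study drug-related toxicities have resolved or are determined to be 'chronic' or 'stable', whichever comes first". A new anticancer therapy also ends the period.

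Section 11.5.1.4 gives a different end. The period "begins upon signing of informed consent and ends 28 days after the last study treatment administration". Every event in it must be reported, related or not. The one exception is a new anticancer therapy begun within the 28 days, when "the adverse event reporting period will end at the time the new anticancer therapy starts".

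Other passages bear on the same period:

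- Section 10 requires adverse event follow-up for a minimum of 28 days after the last dose.
- The unnumbered closing notes under Tables 2 and 4 also end the reporting period at 28 days. They then continue follow-up of unresolved serious and unresolved related events.
- Section 11.5.1.5 covers that later stage: "The following events should be followed after the end of the reporting period", namely unresolved serious events and unresolved related non-serious events.

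Footnote 16 of both tables has a similar early exit for concomitant medications: "or until all study drug-related toxicities have resolved, whichever comes first". Section 9.2.7 collects them for 28 days, or up to 35 where applicable, with no exit on resolution.

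**The concern.** Footnote 17 makes the end of recording depend on the patient's current toxicity status. A patient with nothing serious or related still open already meets the condition, so the footnote permits recording to stop at once. The other statements of the rule do not.

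The body text does not clearly settle the conflict. Section 11.5 refers to the Schedule for safety assessments, and section 10 refers to it for the data collected at end of treatment. No rule says which text prevails.

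Two things are at stake:

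- **Completeness of safety data.** Safety is a secondary endpoint of a single-arm trial. New events between early closure and day 28 could be recorded at one site and not at another.
- **Reporting of deaths.** Section 11.5.1.1.2 makes every death within the reporting period a serious adverse event, including death from progression. After the period, section 11.5.1.5 asks only for suspected serious reactions and deaths that the investigator believes are related. Where the period closes therefore decides whether a death judged unrelated must be reported as a serious adverse event.

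**Working it through.** The plan gives no figure to reproduce, so this is a comparison of rules. Count days from the last dose. Let R be the day on which all serious or related toxicities are resolved, chronic or stable (R = 0 if none is open at the last dose). Let N be the day a new anticancer therapy starts.

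| Source | End of recording |
|---|---|
| Section 11.5.1.4 | min(28, N) |
| Section 10 | at least 28 |
| Closing notes, Tables 2 and 4 | 28, then follow-up of unresolved serious or related events |
| Footnote 17, Tables 2 and 4 | min(28, R, N) |

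**No new therapy before day 28.** Section 11.5.1.4 gives 28 and footnote 17 gives min(28, R). The shortfall is 28 − R when R is below 28, and otherwise zero.

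- R = 0: 28 − 0 = 28 days.
- R = 28 or later: 0 days.

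The literal range is 0 to 28 days.

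**New therapy before day 28.** Both rules include N, so they agree on that exit. They differ only if R falls before N.

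**Related event still open at day 28.** Footnote 17 and section 11.5.1.4 both end recording at day 28. Section 11.5.1.5 and the closing notes then take over. There is no conflict in this case.

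**Death on day 20, judged unrelated, with R before day 20 and no new therapy (an illustration).** Under section 11.5.1.4 the period is still open, so the death is a serious adverse event. Under footnote 17 the period has closed and section 11.5.1.5 does not require the report. The death would still be captured by survival follow-up, so overall survival is unaffected; what changes is the safety report.

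**Footnote 16.** The same comparison applies. Section 9.2.7 gives 28 days (at most 35), while the footnote can end when related toxicities have resolved.

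**The case against.** The strongest reply is that one loose clause stands against several clear statements, one of them in the same block of footnotes. A site using only the Schedule still sees the 28-day period and the later follow-up in the closing notes. Adverse events are a listed assessment at end of treatment and at the visit 28 to 35 days after discontinuation. Section 11.5.1.3 has each patient asked at every clinic visit about health problems since the last one, so the 28-day visit looks back over the interval. Hematology and chemistry are also scheduled at both visits. All of this stands, and it limits the practical risk.

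It could also be said that the earlier-of phrase in footnote 17 only chooses between resolution and a chronic or stable state. The sentence does not read naturally that way, and footnote 16 uses the same phrase with no chronic or stable alternative. There it can only choose between the time limit and resolution.

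A reader might infer three stronger things that the documents do not support:

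- **That late toxicity is lost.** Loss requires a site to follow the footnote against the closing notes, section 10 and section 11.5.1.4.
- **That the footnote contradicts section 11.5.1.5.** That section governs follow-up after the reporting period, and the closing notes restate it.
- **That the whole 28 days would typically go unrecorded.** This is the extreme of a literal reading and ignores the scheduled visits.

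An effect on the Grade 4 hold rule in section 12.4 or on the safety board's review is conceivable, but nothing in the documents allows it to be estimated.

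**Conclusion.** Footnote 17 is wrong as written in both tables. It permits recording to end before day 28 on a condition that section 11.5.1.4, section 10 and the closing notes do not contain. Footnote 16 has the same fault against section 9.2.7.

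The literal shortfall is 0 to 28 days per patient. That is a bound, not an expected loss, and the documents give no basis for an expected figure. The exposure is mainly new events arising between early closure and day 28 that the look-back question does not recover, and deaths in that interval judged unrelated. It rests on the assumption that at least some sites apply the footnote literally.

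This is an internal inconsistency in data collection, inexpensive to correct, and does not show that the safety data will be deficient. Because Phase I ended on 30 May 2022, the practical value lies mainly in Table 4.

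**What to change.** - **Footnote 17, Tables 2 and 4:** delete "or until all serious or study drug-related toxicities have resolved or are determined to be 'chronic' or 'stable', whichever comes first". State that all adverse events are recorded until 28 days after the last dose or the start of a new anticancer therapy, whichever is earlier, with later follow-up of unresolved serious and related events as in section 11.5.1.5 and the closing notes.
- **Footnote 16, Tables 2 and 4:** delete "or until all study drug-related toxicities have resolved, whichever comes first" and use the period in section 9.2.7 (28 days, if applicable no more than 35). Section 9.2.7 does not mention the new-therapy exit that footnote 16 contains, so the sponsor should make the two agree on that as well.

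The cost is four footnote edits at the next amendment and slightly more adverse event and concomitant-medication data entry. No visit or test is added, because the 28-day visit already exists. If effort has to be limited, Table 4 comes first.
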